7.1.5.1. Statistical Methodology Specification

| Endpoint |
|--|
| 
 Proportion of Participants with plasma HIV-1 RNA ≥ 50 c/mL at Week 48 using the Snapshot algorithm for the ITT-E population. Subjects with 'HIV-1 RNA ≥ 50 c/mL' per Snapshot algorithm include those who had plasma HIV-1 RNA ≥ 50 c/mL at Week 48, who discontinued for lack of efficacy, who discontinued for other reasons while not <50 c/mL, or who changed ART. |

Snapshot Dataset

- Virologic outcome ('HIV-1 RNA <50 c/mL' or 'HIV-1 RNA \geq 50 c/mL') per Snapshot algorithm is determined by the last available on-treatment HIV-1 RNA measurement within the analysis visit window of interest (please refer to analysis window defined in [Table 10](#)). In addition, subjects who discontinue for reasons not related to adverse event with on-treatment HIV-1 RNA result at the time of discontinuation \geq 50 c/mL or who change study treatment not permitted per protocol during maintenance phase before the analysis visit are classified as 'HIV-1 RNA \geq 50 c/mL'.
- Full details of the Snapshot algorithm are provided in [Section 15.9](#).

Model Specification

- The primary efficacy endpoint will be analysed using a stratified analysis with Cochran-Mantel-Haenszel (CMH) weights, adjusting for the rederived randomization strata corresponding to prior exposure to CAB+RPV (0 weeks, 1-24 weeks, >24 weeks)
- The CMH estimate of the adjusted treatment difference will be calculated as a weighted average of strata-specific estimates of the treatment difference calculated within each stratum as follows:
 - If n_k is the number of Q8W treated participants, m_k is the number of Q4W arm treated participants, and $N_k = n_k + m_k$ is the total number of participants in the k th stratum, then the CMH estimate is given by

$$\hat{d}_{cmh} = \frac{\sum W_k \hat{d}_k}{\sum W_k}$$

where

$$W_k = \frac{n_k m_k}{N_k}$$

are CMH weights and \hat{d}_k are estimates of the differences in proportions between the two treatment arms, $f_{Q8W} - f_{Q4W}$, for the k th stratum.

- The corresponding two-sided 95% CI will be calculated as

$$\hat{d}_{cmh} \pm 1.96 \times \sqrt{\text{var}(\hat{d}_{cmh})}$$

where the variance estimator [[Sato, 1989](#)] is consistent in both sparse data and large strata and is given below:

$$\text{var}(\hat{d}_{cmh}) = \frac{\hat{d}_{cmh}(\sum P_k) + \sum Q_k}{(\sum n_k m_k / N_k)^2} = \frac{\hat{d}_{cmh}(\sum P_k) + \sum Q_k}{(\sum W_k)^2}$$

where

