15.6.3. Efficacy

| |
|--|
| Snapshot |
| 
 The Snapshot algorithm is intended to be primarily a virologic assessment of the endpoint, and as such follows a “virology first” hierarchy. ‘HIV-1 RNA < 50 c/mL’ or ‘HIV-1 RNA ≥ 50 c/mL’ within an analysis window (see Table 10 and Table 13) is typically determined by the last available HIV-1 RNA measurement in that window while the participant is On-treatment in the Maintenance Phase (as assigned based on Section 15.4). When no HIV-1 RNA data is available within a window, a participant cannot be assigned to the category of ‘HIV-1 RNA < 50 c/mL’. Depending on the reason for lack of data, the participant will be classified as ‘HIV-1 RNA < 50 c/mL’ or reported as ‘No Virologic Data at Week X’; in the latter case, the algorithm further classifies the nature of the missing data. Typically, a participant withdrawn (i) due to AE or, (ii) for another reason yet was suppressed at the time, will be counted as ‘No Virologic Data at Week X’. Should a participant withdraw for reasons other than AE and was not suppressed at the time, they will be categorized as ‘HIV-1 RNA ≥ 50 c/mL’. Full details of the algorithm, including the handling of special cases, are included in Section 15.9 |
| Plasma HIV-1 RNA |
| 
 For summaries and analyses which use HIV-1 RNA level as a continuous measure, the logarithm to base 10 of the value will be used. HIV-1 RNA results may be provided as censored values, such as <40 or >9,999,999 c/mL. For the purposes of summary statistics, such values will be replaced by the next value beyond the limit of detection, e.g., 39 or 10,000,000 c/mL, respectively, for the given examples. Data listings will show the censored values as provided. |
| Target Detected / Target Not Detected / Super Low Viral Load Testing |
| 
 When a measurement of plasma HIV-1 RNA is below the limit of quantification (i.e. 40 c/mL) and is qualitatively observable that will be denoted as a “Target Detected” measure, while HIV-1 RNA below the limit of quantification that is not qualitatively observable that will be denoted as “Target Not Detected”. Any measurements <40 c/mL characterised as “Target Not Detected” or “Target Detected” will be captured in the database. Super low viral load will also be tested by BioMONTR Labs for viral loads below the limit of quantification at some visits (e.g. Week 48). |

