| 5.2.2.3 Non-safety and Non-COVID-19 related reasons (e.g. Lack of efficacy, protocol deviation, withdrew consent, loss to follow-up, study closed/terminated, investigator discretion etc, as recorded in eCRF Conclusion Form) | | |
| • Last on-treatment VL <50 c/mL OR no on-treatment VL available during study | No virologic Data at Week 48 Window | Disc for other reasons (Non-COVID-19 related) |
| • Last on-treatment VL ≥ 50 c/mL AND withdrawal due to Lack of efficacy | HIV-1 RNA ≥ 50 | Disc. for lack of efficacy (Non-COVID-19 related) |
| • Last on-treatment VL ≥ 50 c/mL AND withdrawal due to all other non-safety related reasons | HIV-1 RNA ≥ 50 | Disc. for other reason while not below 50 (Non-COVID-19 related) |
| 5.2.2.4 Non-safety and COVID-19 related reasons (e.g. protocol deviation, withdrew consent, loss to follow-up, study closed/terminated, investigator discretion etc, as recorded in eCRF Conclusion Form) | | |
| • Last on-treatment VL <50 c/mL OR no on-treatment VL available during study | No virologic Data at Week 48 Window | Disc for other reasons (COVID-19 related) |

| | | |
|--|---------------------|--|
| 
 Last on-treatment VL \geq 50 c/mL AND withdrawal due to Lack of efficacy | HIV-1 RNA \geq 50 | Disc. for lack of efficacy (COVID-19 related) |
| 
 Last on-treatment VL \geq 50 c/mL AND withdrawal due to all other non-safety related reasons | HIV-1 RNA \geq 50 | Disc. for other reason while not below 50 (COVID-19 related) |
| 
a. Excluding permitted change in background therapy where change or decision to change is made prior to/on the first on-treatment viral result
 
b. Including participants who either prematurely withdraw or complete the study per study conclusion form. In this study, participants who completed the Maintenance phase and decided not to enter the Extension phase without the reason beyond the completion of the study commitment are considered completers per study conclusion form.
 | | |

Examples from FDA guidance

Data in Window

Virologic outcome should be determined by the last available measurement while the patient is on treatment and continued on trial within the time window:

- HIV-1 RNA = 580 c/mL at Day 336, HIV-1 RNA below 50 c/mL on Day 350. This should be categorized as HIV-1 RNA below 50 c/mL.

No Data in Window

Discontinued study due to Adverse Event or Death:

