- Any patient who discontinues because of an AE or death before the window should be classified as *Discontinued due to AE or Death* (as appropriate), regardless of the HIV-1 RNA result, even if the HIV-1 RNA is below 50 c/mL at the time of discontinuation.
- However, if a patient has an HIV-1 RNA value in the time window and also discontinues in the time window, the viral load data should be used to classify the patient's response. This is the Virology First hierarchy:
 - HIV-1 RNA below 50 c/mL at Day 336 and discontinues because of AE or even dies on Day 360 — this person is categorized as having HIV-1 RNA below 50 c/mL.
 - HIV-1 RNA is 552 c/mL on Day 336 and the patient discontinues on Day 360, the patient is categorized as having HIV-1 RNA \geq 50 c/mL.

Discontinued for Other Reasons:

- Only patients who have achieved virologic suppression can be counted as *Discontinued for Other Reasons*.
- If a patient discontinues the study before the time window because of *lack of efficacy* then the patient should be included in the HIV-1 RNA \geq 50 row and not in the Discontinued for Other Reasons row.
- If a patient discontinues because *participant withdrew consent* and his or her HIV-1 RNA result at the time of discontinuation was equal to or above 50 c/mL, then he or she should be categorized as HIV-1 RNA \geq 50 and NOT as Discontinued for Other Reasons.

- If a patient discontinued because of *Lost to Follow-Up* and the last HIV-1 RNA result was 49 c/mL, then the patient can be categorized as Discontinued for Other Reasons.
- If patients changed background treatment — *not permitted by protocol*— they should be considered an efficacy failure and captured in the HIV-1 RNA ≥ 50 c/mL row.

On study but missing data in window:

- If there are no data during Days 294 to 377, but there is an HIV-1 RNA below 50 c/mL on Day 380, this patient should be considered *On Study but Missing Data in Window*.
- If there are no data during Days 294 to 377, but there is an HIV-1 RNA equal to or above 50 c/mL on Day 280, this patient also should be classified as *On Study but Missing Data in Window*.

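### The SAP gives two Snapshot outcomes for a lack-of-efficacy withdrawal with no on-treatment viral load in the window and a last value below 50 c/mL (or none)

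*SAP*

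**What the plan says.** **Texts that make this participant a failure (HIV-1 RNA ≥50 c/mL).**

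- Section 7.1.5.1, under Endpoint, includes those "who discontinued for lack of efficacy, who discontinued for other reasons while not <50 c/mL, or who changed ART". The viral-load qualifier is attached to other reasons, not to lack of efficacy.
- The category list at the start of Appendix 9 (Section 15.9) puts discontinuation for lack of efficacy under ≥50 c/mL with no viral-load condition, next to a separate entry for other reasons while not below 50.
- The guidance examples reproduced at the end of Appendix 9 say: "If a patient discontinues the study before the time window because of *lack of efficacy* then the patient should be included in the" ≥50 c/mL "row and not in the Discontinued for Other Reasons row". Another example restricts the other-reasons row to patients who have achieved suppression.

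**Texts that make this participant a non-failure.**

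- Step 5.2.2.3 of the decision table covers "Non-safety and Non-COVID-19 related reasons (e.g. Lack of efficacy, protocol deviation, withdrew consent, loss to follow-up" and further reasons. Its first line, "Last on-treatment VL <50 c/mL OR no on-treatment VL available during study", leads to no virologic data, discontinued for other reasons. Lack of efficacy becomes a failure only on the next line, where a last value ≥50 c/mL is required "AND withdrawal due to Lack of efficacy".
- Step 5.2.2.4 (COVID-19 related) omits lack of efficacy from its example reasons but repeats the same lines, including the lack-of-efficacy one.
- Section 7.1.4 (repeated in 7.2.4), the Snapshot Dataset text of 7.1.5.1 and one sentence of 15.6.3 make a non-AE discontinuation depend on the viral load at that time, without separating lack of efficacy.

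**A related slip.** Section 15.6.3 says a participant without data in the window cannot be placed in the <50 c/mL category. The next sentence begins "Depending on the reason for lack of data, the participant will be classified as" and then names <50 c/mL as one of two possible outcomes. Section 15.7.2.2 states the same rule correctly, with ≥50 c/mL.

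**The concern.** The no-virologic-data category is not a failure for the primary endpoint, so the choice of text decides whether a declared efficacy failure enters the numerator. Two programmers could each follow the SAP and obtain different primary counts.

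The hypothesis in Sections 2.4 and 5.5.1 is framed by the US FDA Snapshot algorithm, and the SAP itself reproduces the guidance example that its table contradicts. Leaving these participants out of the numerator is also the non-conservative reading in a non-inferiority comparison. The same algorithm serves Weeks 24, 96 and 152 and the sub-study.

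**Working it through.** **1. One test case against each text.** Withdrawn for lack of efficacy, no on-treatment viral load in the window, last on-treatment value <50 c/mL.

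| Text | Outcome |
|---|---|
| 7.1.5.1, Endpoint | Failure |
| 15.9, category list | Failure |
| 15.9, guidance examples | Failure |
| 15.9, steps 5.2.2.3 and 5.2.2.4 | No virologic data |
| 7.1.4, 7.2.4, Snapshot Dataset text of 7.1.5.1 | Not named as a failure |
| 15.6.3, sentence on withdrawal while suppressed | No virologic data |

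If there is no on-treatment value at all, the table again gives no virologic data for other reasons. That also conflicts with the example limiting this row to suppressed patients.

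**2. How far the case reaches.** Step 5.1 settles anyone with an on-treatment value in the window, so the conflict is confined to those without one. It can arise: confirmed failure needs two consecutive values ≥200 c/mL (Section 13), and a later on-treatment value below 50 then overrides the recorded reason.

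**3. Comparison with the time-to-event rule.** In Appendix 10, withdrawal for lack of efficacy is an event in the efficacy-related analysis with no viral-load condition. The same person can be an efficacy failure there and a non-failure in the primary endpoint.

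**4. Scale.** The SAP states no figure that depends on this rule, so there is none to reproduce. Inputs: 510 per arm (Section 1, protocol amendment 1), margin 4% (Section 2.4), and the difference and Sato variance of Section 7.1.5.1, collapsed to one stratum. Failure counts are assumptions.

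- One participant: 1/510 = 0.196 percentage points.
- With x failures in Q8W, y in Q4W and n = m = 510: W = 510 × 510/1020 = 255; P = (y − x)/4; Q = [x(510 − y) + y(510 − x)]/(2 × 1020); variance = (d·P + Q)/W².
- x = y = 10: d = 0, Q = 4.902, SE = √4.902/255 = 0.868%, upper bound = 1.96 × 0.868 = 1.70%.
- x = 11, y = 10: d = 0.196%, upper bound 1.94%. With 2, 3 and 5 extra: 2.18%, 2.41% and 2.88%.
- x = 20, y = 10: d = 1.961%, P = −2.5, Q = 7.304, SE = √(7.304 − 0.049)/255 = 1.056%, upper bound = 1.961 + 2.070 = 4.03%. Non-inferiority is lost at 10 extra Q8W failures.
- For 5, 15 and 20 base failures per arm, the number needed is 12, 9 and 8.

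A shortcut that keeps the equal-rates half-width is too generous. At 2% it is 1.96 × √(2 × 0.02 × 0.98/510) = 1.72 points, which suggests room for 4 − 1.72 = 2.28 points. With Q8W at its own higher rate, the limit is about 1.92 points, or 1.92% × 510 ≈ 10 participants, in line with the Sato result.

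**5. Sub-study.** With 41 per arm (Section 2.3), one participant is 1/41 = 2.4 points.

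**The case against.** The strongest reply is that the table is the operative rule. Sections 7.1.5.1 and 15.6.3 both point to Section 15.9 for the full algorithm, and 7.1.4, 7.2.4 and the Snapshot Dataset text agree with it. On that view the outliers are a summary line and an example, and editing those would reconcile the plan equally well. It is true that the plan is split, and that lack of efficacy with a last value ≥50 c/mL is a failure under every text. But the category list and the guidance examples stand inside Section 15.9 itself, so deferring to that section does not settle the matter.

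A reader might infer that the rule favours Q8W, because on-treatment values run to 63 days after the last injection there and to 35 days in Q4W (Section 15.4.2). The SAP does not support this. Each allowance is the dosing interval plus 7 days (56 + 7 and 28 + 7), a longer period can equally record a last value ≥50 c/mL, and for participants going into long-term follow-up the phase ends at the start of follow-up ART in both arms (Section 15.4.1).

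Nor does the wording in 15.6.3 show that missing data would be counted as suppressed: the preceding sentence and Section 15.7.2.2 rule that out.

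Finally, Section 5.4.2 shows that the Week 48 data cut has passed, so a changed rule would now alter a primary endpoint already analysed. That stands, and it shapes the fix.

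**Conclusion.** The contradiction is real and sits in the primary endpoint definition, for one narrow group: lack-of-efficacy withdrawals with no on-treatment viral load in the window and a last value <50 c/mL or none. The table's rule is the one to change, because the endpoint text and the reproduced guidance example agree against it and it is the less conservative choice for non-inferiority.

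The SAP does not say how many participants are affected; the number is probably small. Starting from equal arms at an assumed 5 to 20 failures each, with all reclassification in Q8W and none in Q4W, 8 to 12 participants would be needed to cross the margin. The discrepancy alone is unlikely to reverse the conclusion. The case for action is that the primary count should have one definition, not that the result is in doubt.

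**What to change.** - In steps 5.2.2.3 and 5.2.2.4, put a line before the viral-load test: withdrawal due to lack of efficacy is HIV-1 RNA ≥50 c/mL, discontinued for lack of efficacy, regardless of the last on-treatment value. Restrict the existing first line to other reasons.
- Align 7.1.4, 7.2.4, the Snapshot Dataset text of 7.1.5.1 and 15.6.3 with this rule, and change <50 to ≥50 c/mL in the faulty sentence of 15.6.3.
- Apply the same rule to the Week 24, 96 and 152 and sub-study Snapshot analyses.
- For analyses already run, do not replace the result silently. List the affected participants by arm and report the result under both rules.

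The cost is SAP wording, a few lines of code, one listing and a repeat of the affected tables. The failure count may rise slightly.

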15.10. Appendix 10: Variables Defined for Time to Event Analysis

| Programming Instructions for the Kaplan-Meier analysis of treatment-related discontinuation equals failure (TRDF) for Week 24 IDMC / Week 24 / Week 48 / Week 96 Analyses | | |
|---|---------------|--|
| Condition | Censor Status | Event Description/AVAL |
| 1. Participant met CVF event criteria during the Maintenance Phase (based on derived CVF) | CNSR=0 | EVNTDESC=CVF AVAL=Study Day of SVF* *immediately preceding CVF |
| 2. Participant with Maintenance Phase withdrawal due to ' Lack of Efficacy ', ' Treatment Related AE ', ' Intolerability due to Injection ', or ' Protocol Defined Safety Stopping Criteria ' during Maintenance Phase Note: primary reason and/or standardized subreason for discontinuation based on Maintenance Conclusion form in the eCRF. ' Protocol Defined Safety Stopping Criteria ' includes GSK defined liver chemistry stopping criteria, renal toxicity criteria and QTc withdrawal criteria. Treatment Related AE' is defined as participants who have primary reason for withdrawal =AE and who have at least one AE considered drug related and leading to withdrawal/permanent discontinuation of investigational product. | CNSR=0 | EVNTDESC= terms in italic, respectively. For Q4W arm: AVAL= min [Study Day of Maintenance Phase Discontinuation, max (Study Day of Last Injection + 35, Study Day of Last Dose of Oral Study Treatment (CAB+RPV or SOC Bridging) + 1)] For Q8W arm: AVAL= min [Study Day of Maintenance Phase Discontinuation, max (Study Day of Last Injection + 63, Study Day of Last Dose of Oral Study Treatment (CAB+RPV or SOC Bridging) + 1)] Note: Date of Maintenance Phase discontinuation is from the Maintenance Phase Conclusion form in the eCRF. |
| If none of the above conditions met | | |
| 3. Participant with Maintenance Phase withdrawal due to other reasons | CNSR=1 | EVNTDESC='Censored due to Study Discontinuation for Other Reasons' AVAL will be defined as the same as above 2 |

| Programming Instructions for the Kaplan-Meier analysis of treatment-related discontinuation equals failure (TRDF) for Week 24 IDMC / Week 24 / Week 48 / Week 96 Analyses | | |
|---|---------------|--|
| Condition | Censor Status | Event Description/AVAL |
| 4. Participant who did not have premature withdrawal from the Maintenance Phase | CNSR=1 | 
EVNTDESC='Censored due to data cutoff for analysis'
 
AVAL = Study Day of last on-treatment date during the maintenance phase, which is defined as follows:
 
For Q4W arm: min [Study Day of Nominal Week 100 Visit, Study Day of LTFU ART Start Date, Study Day of Last Contact Date at time of analysis, max (Study Day of Last Injection + 35, Study Day of Last Dose of Oral Study Treatment (CAB+RPV or SOC Bridging) + 1)]
 
For Q8W arm min [Study Day of Nominal Week 100 Visit, Study Day of LTFU ART Start Date, Study Day of Last Contact Date at time of analysis, max (Study Day of Last Q8W IM Dose + 63, Study Day of Last Dose of Oral Study Treatment (CAB+RPV or SOC Bridging) + 1)]
 |

| Programming Instructions for the Kaplan-Meier analysis of treatment-related discontinuation equals failure (TRDF) for Week 152 Analysis | | |
|---|---------------|---|
| Condition | Censor Status | Event Description/AVAL |
| 1. Participant met CVF event criteria during the Maintenance and Extension Phase (based on derived CVF) | CNSR=0 | 
EVNTDESC=CVF AVAL=Study Day of SVF* *immediately preceding CVF
 |
| 2. Participant with study withdrawal due to ' Lack of Efficacy ', ' Treatment Related AE ', ' Intolerability due to Injection ', or ' Protocol Defined Safety Stopping Criteria ' | CNSR=0 | 
EVNTDESC= terms in italic, respectively.
 
For Q4W arm: AVAL= min [Study Day of Study Discontinuation, max (Study Day of Last Injection + 35, Study Day of Last Dose of Oral Study Treatment (CAB+RPV or SOC Bridging) + 1)]
 
For Q8W arm: AVAL= min [Study Day of Study Discontinuation, max (Study Day of Last Injection + 63, Study Day of
 |

| Programming Instructions for the Kaplan-Meier analysis of treatment-related discontinuation equals failure (TRDF) for Week 152 Analysis | | |
|--|---------------|---|
| Condition | Censor Status | Event Description/AVAL |
| Study Conclusion form in the eCRF. 'Protocol Defined Safety Stopping Criteria' includes GSK defined liver chemistry stopping criteria, renal toxicity criteria and QTc withdrawal criteria. Treatment Related AE' is defined as participants who have primary reason for withdrawal =AE and who have at least one AE considered drug related and leading to withdrawal/permanent discontinuation of investigational product. | | 
Last Dose of Oral Study Treatment (CAB+RPV or SOC Bridging) + 1]
 
Note: Date of Study discontinuation is from the Study Conclusion form in the eCRF.
 |
| If none of the above conditions met | | |
| 3. Participant with study withdrawal due to other reasons | CNSR=1 | 
EVNTDESC='Censored due to Study Discontinuation for Other Reasons'
 
AVAL will be defined as the same as above 2
 |
| 4. Participant who did not have premature withdrawal | CNSR=1 | 
EVNTDESC='Censored due to data cutoff for analysis'
 
AVAL = Study Day of last on-treatment date, which is defined as follows:
 
For Q4W arm: min [Study Day of LTFU ART Start Date, Study Day of Last Contact Date at time of analysis, max (Study Day of Last Injection + 35, Study Day of Last Dose of Oral Study Treatment (CAB+RPV or SOC Bridging) + 1)]
 
For Q8W arm min [Study Day of LTFU ART Start Date, Study Day of Last Contact Date at time of analysis, max (Study Day of Last Q8W IM Dose + 63, Study Day of Last Dose of Oral Study Treatment (CAB+RPV or SOC Bridging) + 1)]
 |

Note that last injection and last dose of oral study treatment (CAB+RPV or SOC bridging) mentioned in table above are only applied to participants who permanently discontinued from the study treatment. The similar approach will be used to derive for Kaplan-Meier analysis of efficacy-related discontinuation equals failure (ERDF), except that the reason of withdrawal in Condition 2 will be restricted to 'Lack of Efficacy'.

